### 2. STUDY AIMS AND OBJECTIVES

#### 2.1 Aims

- To assess the effectiveness of a short-term financial incentives-based intervention at bringing about behaviour change and improving ICS adherence and asthma control, in the short-medium term, in CYP with asthma.
- 2. To assess the feasibility of study processes, randomisation, and outcome assessments.
- 3. To generate pilot data that can be used to inform the power calculation and design of a definitive RCT of financial incentives in children with asthma.

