#### 7.2 Statistical methods and sample size

As this is a pilot study, a formal sample size calculation is not required. However, the estimated sample size of 50 participants in total is based upon a calculation from unpublished adherence data obtained from Royal Brompton Hospital from 400 children. Mean adherence in the sample was 65% (SD 22%). A Cochrane review of adherence interventions to ICS for asthma found that electronic trackers or reminders led to better adherence of 19% (95% CI 14.47 to 25.26). Based upon this information, to give 80% power to achieve a 19% difference between the intervention group and controls, 21 participants are required per group. The target of 25 per group accounts for participant dropout. This is supported by evidence that as a pilot study, 25 participants per group, with a total of 50 participants is sufficient.

Data analysis will be conducted using the Statistical Package for the Social Services (SPSS). Statistical analysis of quantitative, normally distributed data will be reported with means ± standard deviations (SD) and non-parametric data will be reported as medians with interquartile range. Data will be tested for normality using visual inspection, histograms, and Kolmogorov-Smirnov testing. Parametric tests will be used where possible for normally distributed data and logarithmically transformed data, otherwise appropriate non-parametric tests shall be used. The significance levels for all tests will be set at <0.5.

Categorical data will be reported as proportions. Comparative analysis of variance between 2 groups for continuous data will be performed using the student's t test for normally distributed data and the Mann Whitney U tests for non-normally distributed data and for more than 2 groups the ANOVA or Kruskal Wallis respectively. A comparison of the proportions between groups will be performed using the Pearson Chi 2 tests. Within group analysis the ANOVA test will also be used.

Questionnaire data will be used alongside group comparisons to observe any notable changes or differences between groups.

Qualitative data obtained from the focus groups will be thematically analysed. An independent researcher will aid with the facilitation/analysis of qualitative aspect of the study to ensure there is no bias.

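### A normality check on the trial's own data chooses the summary and test for adherence, so the plan does not guarantee the mean difference and SD that Aim 3 needs

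*Combined protocol and SAP*

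**What the plan says.** Everything on this point is in section 7.2 (Statistical methods and sample size), except the aim it serves.

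- Normality: "Data will be tested for normality using visual inspection, histograms, and Kolmogorov-Smirnov testing". The plan does not say how the three checks are combined, whether arms are examined separately or pooled, or which version of the K-S test applies.
- Summary: "normally distributed data will be reported with means ± standard deviations (SD) and non-parametric data will be reported as medians with interquartile range".
- Test family: "Parametric tests will be used where possible for normally distributed data and logarithmically transformed data, otherwise appropriate non-parametric tests shall be used".
- Two-group comparison: "student's t test for normally distributed data and the Mann Whitney U tests for non-normally distributed data".
- Aim 3 (section 2.1): "To generate pilot data that can be used to inform the power calculation and design of a definitive RCT".

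The sample-size paragraph in the same section works from a mean (65%), an SD (22%) and a difference in means (19 points). No sentence commits the trial to a mean, an SD or a difference with a confidence interval for the primary outcome whatever the normality check shows.

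**The concern.** The primary outcome has no single analysis fixed in advance. Its summary and test are settled after the data have been seen, by a check that involves judgement.

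One of the two results does not serve the trial's purpose. A power calculation for a continuous outcome needs an SD and a difference in means, as the pilot's own calculation shows. If adherence is judged non-normal, the plan yields medians, interquartile ranges and a Mann-Whitney p-value. Adherence is a percentage and may well be skewed, especially if the incentive moves one arm towards the ceiling.

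The log transform is not a good way out. It stretches the lower tail, so it makes left skew worse. It is undefined at 0%, and its SD is not in percentage points.

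**Working it through.** **1. The plan's own figure.** Inputs from section 7.2: difference 19, SD 22, power 80%. Two-sided alpha of 0.05 is assumed.

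n per group = 2 × (1.960 + 0.842)² × 22² / 19² = 2 × 7.849 × 484 / 361 = 21.05.

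This is the stated 21 (22 if rounded up). The inputs are a mean difference and an SD, so these are what a successor calculation will need.

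**2. What each branch yields.**

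| | Judged normal | Judged non-normal |
|---|---|---|
| Per-arm summary | mean, SD | median, IQR |
| Test | t test | Mann-Whitney U |
| Difference with CI | not named | not named |
| SD for the next power calculation | yes | no |

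On the normal branch the difference and its CI can be derived from the reported means and SDs. On the other branch they cannot.

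**3. How often the non-normal branch might be taken.** Assumptions, none of them in the plan: adherence lies between 0 and 100 with a beta distribution matched to the mean and SD; K-S at 0.05 is applied to each arm of 25; rejection in either arm sends the outcome to the non-normal branch. Only the 65%, the SD of 22 and the 19-point difference come from the documents. The means of 46 and 75, and the SDs of 15 and 20, are assumed. So is placing 65% in the control arm, which makes the other arm 65 + 19 = 84. The alternative is 65 − 19 = 46 in the control arm.

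| Scenario, mean (SD) | Lilliefors-corrected | Uncorrected |
|---|---|---|
| 46 (22) v 65 (22) | about 20% | below 1% |
| 65 (22) v 65 (22) | about 27% | below 1% |
| 65 (22) v 75 (20) | about 46% | about 1% |
| 65 (22) v 84 (15) | about 65% | 2–3% |
| 65 (22) v 84 (22) | about 98% | 37–44% |

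The ranges in the last column reflect the choice of critical value and simulation error. With two truly normal arms, the corrected test still rejects in at least one arm about 10% of the time, as two tests at 0.05 should: 1 − 0.95² = 0.0975.

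**4. Whether medians can stand in.** At 65 (22) v 84 (22), the beta distributions have medians of about 68 and 95. The median difference is about 27, against a mean difference of 19. Dividing the IQR by 1.35 gives spreads of about 25 and 17, not 22 and 22. Used as planning inputs:

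n per group = 7.849 × (25² + 17²) / 27² = 7.849 × 914 / 729 = 9.8, so about 10.

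The mean and SD give 21 to 22. The median route would lead to a definitive trial of less than half the size.

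**5. The log transform.** For the beta distribution at 65% (SD 22), skewness goes from about −0.5 to about −1.8 after logs.

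**6. What routine reporting would give.** With SD 22 and 25 analysed per arm, the standard error of the difference is 22 × √(2/25) = 6.22, and the 95% half-width is 2.011 × 6.22 = 12.5 points. The 95% CI for the pooled SD is about 18.3 to 27.5. With 21 per arm the half-width is 2.021 × 6.79 = 13.7 points, and the CI for the SD is 18.1 to 28.1.

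**The case against.** The strongest reply is that no information is lost. Individual adherence records are collected and stored for 10 years (section 6, Study completion). The same team can compute a mean and SD whenever it likes, and section 7.2 does not forbid reporting them alongside medians. That stands: the gap is in prespecified reporting, not in data collection.

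A reader might infer that the K-S test decides the matter and that the pilot will probably end without the quantities Aim 3 needs. The documents support neither reading. K-S is one of three checks, and the preference for parametric tests could keep the analysis on the mean scale. At the only mean and SD the plan gives, applied to both arms, even the corrected test leaves about 73% of simulated trials on the normal branch. A control mean near 50% is plausible, since section 1.1 says adherence below 50% is common, and rejection is then less frequent. Section 7.2 gives a mean and SD but no shape, so left skew is itself an assumption.

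The missing confidence interval is not caused by the normality check, because the normal branch names none either. Error control is also not the issue: in simulation under no difference, the two-stage rule rejected in 5.7% of trials against 5.1% for Welch alone. Welch and Mann-Whitney disagreed on significance in 2% to 13% of trials, depending on the scenario, which is modest for a pilot.

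What the reply does not remove is the rule itself. Followed as written, the non-normal branch gives medians and a Mann-Whitney test, and the choice of branch is made with the data in view.

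**Conclusion.** The point holds as a failure to guarantee. Section 7.2 fixes neither the summary nor the test for adherence in advance. On one of its two branches it does not produce the SD and mean difference that Aim 3 and the pilot's own calculation rely on, and on neither does it name a difference with a CI.

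The chance of ending on that branch depends on assumptions: about 20% to 98% with the Lilliefors correction and about 0% to 44% without it. These figures rest on beta-shaped adherence, 25 per arm, testing each arm separately and K-S deciding alone at 0.05. They show that the outcome is open, not that it is probable. The distortion from using medians instead (about 27 points against 19) also rests on the beta shape.

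One separate matter bears on this. The plan prints "The significance levels for all tests will be set at <0.5". The sample size fits 0.05, so this looks like a misprint. Applied literally to the normality test, it would reject in at least one of two truly normal arms about 75% of the time with the Lilliefors version (1 − 0.5² = 0.75).

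This is a cheap improvement to the reporting plan, not a threat to the trial's validity.

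**What to change.** Amend section 7.2 for the primary outcome only:

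- For electronically monitored adherence, report the mean and SD in each arm and the difference in means with a 95% CI (Welch or bootstrap, with the choice stated in advance). Make this the primary analysis whatever the normality check shows.
- Add medians with interquartile ranges as supplementary description, and Mann-Whitney U as a sensitivity analysis.
- State that the general log-transform option does not apply to adherence.

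The cost is a few sentences. Sample size, visits and data collection do not change, and the quantities come from the same data. The one drawback is that a mean-based interval is approximate for skewed, bounded data at about 25 per arm; the bootstrap and the Mann-Whitney sensitivity analysis address that.

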#### **OUTCOME MEASURES Primary outcome:**

Percentage ICS adherence (measured by EMD record of inhaler actuation%)

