#### Secondary outcomes:

- Proportion of participants achieving good asthma adherence (≥80%)
- Time to next asthma exacerbation needing a course of oral corticosteroids (OCS)
- Total number of severe exacerbations
- Asthma control (Asthma Control Test, ACT)
- Exhaled nitric oxide (FENO)
- Belief in Medicine Questionnaire (BMQ)
- Brief Illness Perceptions Questionnaire (B-IPQ)
- Habit (self-report behavioural automaticity index, SRBAI)
- Autonomous/controlled motivation (adapted from the Treatment Self-Regulation Questionnaire, TSRQ, for the purpose of this study)
- Self-report adherence (Medication Adherence Report Scale for Asthma, MARS-A)

**POPULATION** CYP aged 11-17 years with an asthma diagnosis

ELIGIBILITY

- CYP aged between 11-17 years old
- A doctor diagnosis of asthma
- Presenting to an emergency department (ED) with a severe exacerbation of asthma (defined by ERS/ATS guidelines\*)
- Own their own smartphone (running Android 8 or higher, or iOS 13 or higher)
- Prescribed maintenance inhaled corticosteroids (ICS) (which can include maintenance and reliever therapy (MART)) for at least 6-months.
- Prescribed one of the following inhalers: Clenil, Flixotide, Symbicort, Seretide.
- **DURATION** Up to 24-weeks (participants will also be involved in a focus group at the end of the study period)

\* Severe exacerbation of asthma: Asthma attack requiring a course of systemic corticosteroids (either prednisolone or dexamethasone), or hospital admission 

Research Governance and Integrity Team

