#### 2.2 Objectives

- 1. To recruit children and young people aged between 11-17 years with asthma and measure adherence using EMDs (programmed with reminders) and a self-report measure (MARS-A) during a 12-week intervention period when financial incentives are given and compare to a group given an EMD (programmed with reminders) only, and to continue to measure adherence during a subsequent 12-week period (when no financial incentives are given) to assess whether financial incentives lead to continued better adherence in the short-medium term compared to the control group.
- 2. To measure asthma outcomes (number of severe exacerbations, time to exacerbation, asthma symptoms and if feasible given COVID-19 constraints, exhaled nitric oxide) at baseline, 12-weeks, and 24-weeks to assess whether financial incentives lead to short-medium term changes in a range of asthma control measures compared to the control group.
- To measure habit (using the self-report behavioural automaticity index, SRBAI) and autonomous/controlled motivation (using a questionnaire adapted from the Treatment Self-Regulation Questionnaire (TSRQ)) at baseline, 12-weeks, and 24-weeks to

Research Governance and Integrity Team

assess whether financial incentives lead to short-medium term changes in medication taking habits and motivations compared to the control group.

- 4. To measure beliefs in medicine (using Beliefs in Medicines Questionnaire, BMQ) and perceptions of illness (using the Brief-Illness Perceptions Questionnaire, B-IPQ) at baseline, 12-weeks, and 24-weeks to assess whether financial incentives lead to short-medium term changes in beliefs and perceptions regarding medication and illness and compared to the control group.
- 5. To conduct focus groups with participants from both the intervention and the control group and interviews with parents/guardians using a topic guide to obtain feedback of the trial and inform the design of a larger RCT.

Research Governance and Integrity Team

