#### 3.1. STUDY OUTCOME MEASURES

Primary outcome:

• ICS adherence (measured by EMD record of inhaler actuation%)

Secondary outcome:

- Proportion of participants achieving good asthma adherence (≥80%)
- Time to next asthma exacerbation needing a course of oral corticosteroids (OCS)
- Total number of severe exacerbations (incident rate ratio)
- Asthma control (measured by asthma control test (ACT))
- FENO
- Habit (measured by Self-Report Behavioural Automaticity Index, SRBAI)
- Belief in Medicines Questionnaire (BMQ)
- Brief Illness Perception Questionnaire (B-IPQ)
- Autonomous/controlled motivation (adapted from the Treatment Self-Regulation Questionnaire, TSRQ)
- Self-report adherence (Medication Adherence Report Scale for Asthma, MARS-A)

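### Section 7.2 sets the significance level for all tests at <0.5, almost certainly a slip for 0.05; no other alpha is stated, and 0.5 does not fit the plan's own 21 per group

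*Combined protocol and SAP*

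**What the plan says.** Section 7.2 (Statistical methods and sample size) gives one decision rule for every test: "The significance levels for all tests will be set at <0.5". The only related figure is a 95% CI taken from a cited review, which is not a decision level for this trial.

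The same section gives the sample-size basis: "Mean adherence in the sample was 65% (SD 22" percentage points), an expected difference of 19 points, and the statement that "to give 80% power to achieve a 19% difference between the intervention group and controls, 21 participants are required per group". It gives neither alpha nor sidedness for that calculation. The target is then raised to 25 per group for dropout. For continuous outcomes, the two-group comparison is to be "performed using the student's t test for normally distributed data and the Mann Whitney U tests for non-normally distributed data"; proportions are compared by Pearson chi-square.

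On the separate matter of timing, the Study Summary defines the primary outcome as "Percentage ICS adherence (measured by EMD record of inhaler actuation" %), and section 3.1 defines it in nearly the same words. Neither gives a period. Objective 1 in section 2.2 compares the arms over the 12-week incentive period and then plans "to continue to measure adherence during a subsequent 12-week period (when no financial incentives are given").

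**The concern.** A threshold of 0.5 does not control error in any useful sense. Aim 1 in section 2.1 is to assess effectiveness, section 7.2 lists formal tests, and this sentence is the only written rule for calling a result significant. If it were applied or quoted as written, differences well within chance would be reported as positive findings, and aim 3 carries the pilot data forward into the design of a definitive trial.

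A reader can guess that 0.05 was meant but cannot confirm it from the text. Nor can a reader tell whether the tests are one-sided or two-sided.

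The missing window raises a different risk. The choice between weeks 0-12, weeks 13-24 and the full 24 weeks stays open until the data have been seen.

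**Working it through.** **Inputs.** From section 7.2: SD 22 points, difference 19 points, power 80%, 21 per group required, 25 per group planned, alpha <0.5 for all tests. From section 3: 1:1 allocation. Sidedness is not stated; two-sided is assumed and one-sided was also tried.

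**1. Reproducing the plan's 21 per group.** Normal approximation for two means:

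n per group = 2 × (z for 1 − α/2 + z for 0.80)² × SD² / difference²

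- α = 0.05 two-sided: 2 × (1.960 + 0.842)² × 22² / 19² = 21.05, which matches the stated 21.
- α = 0.5 two-sided: 2 × (0.674 + 0.842)² × 22² / 19² = 6.16, so 7 per group (6 by exact t).
- α = 0.05 one-sided (the same as 0.10 two-sided): 16.6, so 17 per group.

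Among alphas of 0.5, 0.1, 0.05, 0.025 and 0.01, each one-sided and two-sided, only two-sided 0.05 and its equivalent, one-sided 0.025, reproduce 21.

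**2. Solving for the alpha implied by 21 per group and 80% power.** The standardised difference is 19 / (22 × √(2/21)) = 2.80. Subtracting 0.842 leaves 1.957, a two-sided alpha of 0.0504. The exact t calculation gives 0.058.

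**3. Power.**

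| Two-sided alpha | n per group | Normal | Exact t |
|---|---|---|---|
| 0.05 | 21 | 79.9% | 78.0% |
| 0.05 | 25 | 86.3% | 84.9% |
| 0.5 | 21 | 98.3% | 98.3% |

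At 0.5, the plan's 21 per group would have 98% power, not the 80% stated.

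**4. Smallest observed difference that counts as significant (t test, SD 22).** Critical difference = t critical × 22 × √(2/n).

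| n per group | Standard error | At 0.5 | At 0.05 |
|---|---|---|---|
| 25 | 6.22 | 0.680 × 6.22 = 4.2 points | 2.011 × 6.22 = 12.5 points |
| 21 | 6.79 | 0.681 × 6.79 = 4.6 points | 2.021 × 6.79 = 13.7 points |

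An observed 4.23 points with 25 per group has a 95% CI of 4.23 ± 12.51, that is -8.3 to 16.7.

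**5. The outcome of adherence at or above 80%.** Pearson chi-square, 25 per group, no continuity correction. The control counts are assumed, because the plan gives none.

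| Control count | Needed in the other arm for p<0.5 | Needed for p<0.05 |
|---|---|---|
| 5 | 8 | 12 |
| 8 | 11 | 15 |
| 10 | 13 | 17 |
| 12 | 15 | 19 |

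For every control count from 5 to 12, three more responders are enough at 0.5, against seven more at 0.05.

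**6. Time window (secondary).** If both 12-week periods were tested as primary at 0.05, the chance of at least one false positive would be 9.8%, 9.1% or 7.8% for assumed correlations between the two tests of 0, 0.5 or 0.8. The plan does not say that both would be tested as primary.

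**The case against.** The strongest reply is that this is an obvious typing error in a pilot, that nobody will use 0.5, and that the 50% false-positive rate is therefore hypothetical. Nothing in the documents suggests the team intends 0.5, and the section says that a pilot needs no formal sample-size calculation. This limits the likely harm, but it does not remove the need to correct the sentence. It is the only stated decision rule, it covers all tests, effectiveness is the first aim, and the section goes on to give a powered calculation.

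It is also fair to say that 0.05 is inferred. The sample-size sentence states no alpha, so two stated values are not in conflict. The match is very close by the normal approximation (0.0504) and looser by the t test (0.058).

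Two qualifications on size stand. The rate of about 50% is for continuous tests; for the chi-square at 25 per group the actual rate is roughly 46% to 52% over true proportions of 0.2 to 0.48. The 4.2-point threshold assumes a t test with SD 22, whereas non-normal adherence data would go to Mann-Whitney.

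It is also right that correcting alpha does not vindicate 25 per group. The exact t calculation needs 22.05, so 23 per group, leaving 2 of 25 (8%) for dropout. If adherence data were lost at the rate in the feasibility study described in section 1.2 (8 of 10 provided them to the final visit), 20 per group would remain, with about 76% power. The 19-point effect is for electronic trackers or reminders, which both arms receive here. These points bear on the sample-size assumptions and are not settled by the alpha correction.

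Finally, the window is a separate matter. Objective 1 distinguishes the two periods and the section 6 schedule lists electronic adherence at 12 and 24 weeks, but neither is designated primary.

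**Conclusion.** The concern holds, and the sentence must be corrected before analysis. It is wrong as written: the level is ten times the one implied by the plan's own figures, and no other statement overrides it. Used literally, it would lower the t-test threshold at 25 per group from 12.5 to 4.2 points of adherence, and the requirement for the 80% adherence outcome from seven extra responders to three. These sizes rest on SD 22, 25 analysed per group, two-sided tests and, for the responder outcome, assumed control counts of 5 to 12. That 0.05 was intended is an inference, though a strong one.

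The missing primary window is a genuine but lesser gap, and the conclusion about alpha does not depend on it.

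**What to change.** In section 7.2, change the level for all tests to <0.05 (two-sided), and add the same alpha and sidedness to the sample-size sentence. The alpha correction alone does not alter the planned 25 per group.

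Separately, add one line to section 3.1, repeated in the Study Summary, naming a single primary window and comparison before any analysis. Weeks 0-12, weeks 13-24 and the full 24 weeks are each defensible, and the choice belongs to the investigators. Report the other periods as exploratory with 95% CIs.

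The cost is a wording change in section 7.2 and one line on the window, with no operational change.

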#### 4.4. WITHDRAWAL CRITERIA

CYP will be withdrawn from the study if CYP/parent/guardian refuse or withdraw their consent to participate in the study. Parent/guardian/CYP can refuse intervention, adherence monitoring or any study tests/questionnaires at any time without any negative consequences. Participation or withdrawal in the study will not affect the patient's clinical care and participants will not be prevented from receiving any treatment that may be required without participating in the study.

We don't anticipate any reason to stop the trial or other research early.

Any data already collected from a participant who decides to withdraw from the study will be kept. If a participant decides to withdraw from the study, data already collected until that point in the study will be used.

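### Does section 7.2 need to name a survival method and a rate model for the two exacerbation outcomes?

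*Combined protocol and SAP*

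**What the plan says.** Section 3.1 lists ten secondary outcomes. Two concern attacks: "Time to next asthma exacerbation needing a course of oral corticosteroids (OCS") and "Total number of severe exacerbations (incident rate ratio"). Objective 2 in section 2.2 covers both, beginning "To measure asthma outcomes (number of severe exacerbations, time to exacerbation, asthma symptoms", and compares them with the control group.

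Section 7.2 is the only statistical section. Its sentence on two-group comparisons runs "Comparative analysis of variance between 2 groups for continuous data will be performed using the" t test when the data are normal and Mann-Whitney when they are not, with ANOVA or Kruskal-Wallis for more than two groups. For proportions it gives Pearson chi-square. It also has a general fallback: "otherwise appropriate non-parametric tests shall be used". Its summaries are means with SDs, proportions, and for skewed data "non-parametric data will be reported as medians with interquartile range".

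No section names Kaplan-Meier, log-rank, Cox, Poisson or negative binomial methods. None states a time origin, a censoring rule or a person-time offset. The nearest text is in section 4.4: "If a participant decides to withdraw from the study, data already collected until that point in the study will be used".

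**The concern.** A time to event in a 24-week study is censored for every child who reaches week 24 or leaves without an attack. A rate ratio needs events divided by person-time. None of the tests that section 7.2 names does either. If the rule for continuous data were applied mechanically, a child followed for 24 weeks without an attack would be given an event time of 24 weeks. A child who withdrew at week 6 would look like an early relapse.

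The summaries raise a similar worry. Most children would have no attack, so a median count would often be 0 in both arms even if the rate had been halved.

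At stake is the exacerbation part of objective 2, and whether the pilot yields event rates that a definitive trial could use (aim 3 in section 2.1).

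**Working it through.** **Inputs from the documents.** 25 per arm, 1:1 allocation, 24 weeks of follow-up. Section 7.2 gives 21 evaluable per group, raised to 25.

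**The plan's own figure.** With SD 22, a difference of 19, two-sided 0.05 and 80% power:

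n = 2 × (1.960 + 0.842)² × 22² / 19² = 21.05 per group.

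This agrees with the stated 21, at which power is 79.9%. It also shows that the sample size was worked out at 0.05, which is used below. The implied dropout is 1 − 21/25 = 16%. No event count or power is stated for either exacerbation outcome.

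**Assumptions not in the documents.** Control 24-week risk p of 30, 40 or 50%; hazard or rate ratio 0.5; exponential event and dropout times.

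**How many children are censored.**
- Event rate in control: λ = −ln(1 − p)/24 per week, halved in the intervention arm.
- Dropout rate: μ = −ln(0.84)/24 = 0.00726 per week.
- Expected first events per arm: 25 × λ/(λ + μ) × [1 − exp(−24(λ + μ))].
- At p = 30%, control: 25 × 0.6717 × 0.4120 = 6.92. Intervention: 25 × 0.5056 × 0.2972 = 3.76.
- 95% limits for the hazard ratio: the estimate multiplied or divided by exp(1.96 × √(1/d₀ + 1/d₁)), where d₀ and d₁ are the events per arm.

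| Control risk | First events, control v intervention | Censored of 50 | Factor for 95% limits |
|---|---|---|---|
| 30% | 6.92 v 3.76 | 39 | 3.51 |
| 40% | 9.24 v 5.19 | 36 | 2.93 |
| 50% | 11.59 v 6.75 | 32 | 2.58 |

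For 80% power at a hazard ratio of 0.5, the Schoenfeld formula asks for 4 × (1.960 + 0.842)² / (ln 0.5)² = 65.3, so 66 events. About 11 to 18 are expected.

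**What the unfavourable reading would cost, time to event.** Simulated power at hazard ratio 0.5, for control risks of 30/40/50%:

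| Setting | Log-rank | Mann-Whitney on follow-up times | Loss (points) |
|---|---|---|---|
| No dropout | 21.1/26.0/32.0% | 20.1/25.2/30.5% | 1.0/0.8/1.5 |
| 16% dropout, follow-up known to the day | 19.7/25.4/31.2% | 13.5/17.9/22.9% | 6.2/7.5/8.3 |
| 16% dropout, attacks learned only at weeks 12 and 24 | 20/22/29% | 15/19/24% | 5/3/5 |

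The first two rows use 10,000 trials per scenario and the third 4,000. The third row may be nearer to the data collection, because sections 3 and 6 collect asthma history at the visits. The case report form is not shown, so this is a reading.

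Type I error of Mann-Whitney is 4.8/4.8/4.7% with 16% dropout in both arms. With 20% against 12% dropout it is 6.5/6.1/6.1%, and nothing in the documents predicts such an imbalance.

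**The same for counts.** Mean follow-up with 16% dropout is 0.16/0.00726 = 22.0 weeks. Expected attacks at p = 30% are 25 × 0.01486 × 22.0 = 8.2 in control and 4.1 in the intervention arm.
- Power of a Poisson test with person-time offset: 20.4/28.5/36.8%.
- Power of Mann-Whitney on raw counts: 19.7/25.9/31.6%, a loss of 0.7/2.6/5.2 points.
- Both medians are 0 in 99/91/65% of trials. A median would therefore be a poor summary, but section 3.1 names the rate ratio instead.

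**How much the analyst's choice of model matters.** The factor for the 95% limits of the rate ratio is 3.28/2.70/2.34 under Poisson. It is 3.37/2.80/2.46 if children vary in their rates with an assumed gamma variance of 1. The interval is wide under either model.

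**The case for a change.** The best argument for a change is about discretion. Section 7.1 gives data collection and analysis to the study coordinator, with the chief investigator assisting. The same coordinator sees adherence data and works out rewards, so is not blind to allocation. Leaving origin, censoring and model open lets them be chosen after the data are seen. The first visit falls 2 to 12 weeks after the index attack, so the clock could start at two different points. The schedule in section 6 has no row for exacerbation dates. Two or three sentences would settle all of this at almost no cost, and aim 1 is about effectiveness, so the pilot label does not excuse the gap.

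The omission is real, and no other section fills it. A careful author would have written those sentences. But the choices are narrow:

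- **Origin.** A comparison of randomised arms starts at randomisation, which takes place at visit 1. Attacks before that cannot be effects of the incentives.
- **Censoring.** Section 4.4 keeps data up to withdrawal, which leads to censoring there, at loss to follow-up or at week 24. A child who refuses only the incentives or the monitoring, as section 4.4 allows, can still be followed for attacks and need not be censored.
- **Model.** An incident rate ratio is by definition a ratio of events over person-time. Poisson and negative binomial regression with log follow-up time as offset are the usual ways to estimate it, and the intervals above differ little.
- **Dates.** Asthma history is taken at all three visits. The documents do not show whether that form asks for dates, so its absence cannot be inferred.

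The argument that censored times would be read as events needs a rule that the plan does not contain. Section 7.2 confines the t test and Mann-Whitney to continuous data and leaves room for other tests. The argument about medians likewise requires the analyst to ignore the effect measure named in section 3.1.

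**Conclusion.** No change to the plan is needed. Section 7.2 leaves out detail for two of ten secondary outcomes; it does not prescribe a wrong method. The fallback clause can admit a log-rank test, the rate ratio is already named, and section 4.4 implies that partial follow-up is used.

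If the poorer test were nevertheless used for time to event, the cost would be about 1 point of power without dropout and roughly 3 to 8 points with 16% dropout. For counts with 16% dropout it would be about 1 to 5 points. Type I error would stay near 5% under equal dropout. Even the better methods reach only about 20 to 37% power, and their 95% limits lie a factor of about 2.3 to 3.5 either side of the estimate. In practice both outcomes are descriptive at this sample size, whichever test is used.

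These sizes rest on an assumed control risk of 30 to 50%, a single assumed effect (ratio 0.5), exponential times, and a dropout figure taken from the allowance made for the primary outcome. Markedly unequal dropout would weaken the conclusion on Type I error. The primary adherence analysis and the 21 per group do not depend on any of this.
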